### **7.2. Laboratory Evaluations**

Laboratory data collected during the study will be analyzed and summarized using both quantitative and qualitative methods. Summaries of laboratory data will be provided for the Safety Analysis Set and will include data collected up to the last dose of study drug plus 7 days for participants who have permanently discontinued study drug, or all available data at the time of the database snapshot for participants who were ongoing at the time of an interim analysis. The analysis will be based on values reported in conventional units. When values are below the LOQ, they will be listed as such, and the closest imputed value will be used for the purpose of calculating summary statistics as specified in [Section 3.7](#). Hemolyzed test results will not be included in the analysis, but they will be listed in by-participant laboratory listings.

A by-participant listing for laboratory test results will be provided by participant ID number and time point in chronological order for hematology, serum chemistry, and urinalysis separately.

No formal statistical testing is planned.

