## 2. INTRODUCTION

### 2.1. Background on Intrahepatic Cholestasis of Pregnancy

Intrahepatic cholestasis of pregnancy (ICP) is a rare cholestatic disorder that occurs during pregnancy and is associated with maternal changes in liver function, elevated levels of serum bile acids (sBAs), and intractable pruritus, as well as adverse perinatal outcomes ([EASL 2009](#); [Geenes and Williamson 2009](#); [Williamson and Geenes 2014](#); [Ozkan et al. 2015](#); [Wood et al. 2018](#)). Cholestasis refers to an impairment of bile secretion and/or bile flow, which may clinically present with symptoms such as pruritus, fatigue, and jaundice and may be associated with changes in liver biochemistry markers. Intrahepatic cholestasis is defined as cholestasis resulting from hepatocellular functional defects or obstructive lesions of the intrahepatic biliary tract distal from bile canaliculi.

ICP is characterized by pruritus, which is frequently intense and intractable, with typical onset in the second or third trimester of pregnancy and elevated serum aminotransferases and sBA levels. ICP is also frequently associated with an abnormal maternal metabolic profile. In addition to the hepatic features, there is an increased prevalence of dyslipidemia and impaired glucose tolerance in patients with ICP ([Martineau et al. 2015](#)). Gestational diabetes and preeclampsia also occur more commonly in women with ICP ([Goulis et al. 2004](#); [Martineau et al. 2014](#)). After delivery, there is rapid (within a few weeks) resolution of signs and symptoms.

ICP is also associated with an increased risk for adverse perinatal outcomes, including preterm birth and life-threatening or even fatal consequences for the fetus, such as stillbirth ([Sepulveda et al. 1991](#); [Williamson et al. 2001](#); [Ovadia et al. 2019](#)).

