#### **10.4.2.3. Laboratory Assessments**

Clinical safety laboratory values will be measured by a central laboratory and, where grading criteria apply, will be graded according to the CTCAE grading scale. Summary statistics for actual values and for changes from baseline will be tabulated for laboratory results by scheduled visit. Graphs of laboratory values over time may also be produced.

Participants with clinical laboratory values outside of the normal reference range at any postbaseline assessment will be summarized, including by the CTCAE and, if necessary, other grading scales. Shifts from baseline laboratory values will be tabulated. The observed vital sign data, the change from baseline, and those meeting criteria for potentially clinically significantly abnormal criteria for each measurement will be summarized with descriptive statistics.

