### **Part 1: Proof of Concept, Dose Ranging, Pharmacokinetics, and Interim Analysis**

After a screening period of up to 10 days, eligible participants will be identified for one of two cohorts, defined as follows:

- Primary cohort: Participants with ICP with a screening sBA level  $\geq 20$   $\mu\text{mol/L}$  will be randomized with stratification (based on gestational age [ $<32$  weeks or  $\geq 32$  weeks] at randomization, presence/absence of gestational diabetes, and highest sBA before randomization [ $<40$   $\mu\text{mol/L}$ ,  $\geq 40$   $\mu\text{mol/L}$  to  $<100$   $\mu\text{mol/L}$ , or  $\geq 100$   $\mu\text{mol/L}$ ]) in a 3-arm (1:1:1), double-blind fashion to receive volixibat 20 mg BID, volixibat 80 mg BID, or placebo.
- Supplemental cohort: Up to 30 participants with ICP with screening sBA level from  $\geq 15$  to  $<20$   $\mu\text{mol/L}$  will be randomized (based on gestational age at randomization and presence/absence of gestational diabetes) in a 2-arm (1:1), open-label fashion to receive volixibat 20 mg BID or volixibat 80 mg BID.

Study treatment dosing will begin on Day 1 and continue until end of the study treatment period, defined as the day of delivery. Study visits to assess safety, plasma concentrations of volixibat, pharmacodynamics, and efficacy will be conducted weekly from baseline until

delivery. Because alternative measures may be implemented when necessary for public health or other emergency situations, and when sufficient to help ensure the safety of study participants, some visits may be conducted as a home health or remote visit at the discretion of the investigator upon approval by the medical monitor or designee and in accordance with local and regional regulations (see Protocol Appendix 10). Participants will also enter ItchRO assessments into an electronic diary (eDiary) once daily. Use of limited rescue therapies for ICP will be permitted for participants who meet protocol-specified criteria.

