### 3.8.2. Analysis Visit Windows

Participant visits might not occur on protocol-specified days. Therefore, for the purpose of analysis, observations will be assigned to analysis windows. A notable exception to the analysis visit windows below is the end of treatment/date of delivery. This will be summarized as its own visit and that will be the value used for endpoints that look at either the value or change from baseline to delivery.

The analysis windows for ItchRO, sBA, hematology, chemistry, coagulation, weight, vital Signs, and urinalysis are provided in [Table 2](#).

The analysis windows for 5-D Itch, EQ-5D-5L, PROMIS Fatigue and Sleep patient reported outcomes (PROs), PIS-Itch, PGIC-Itch, and Biomarker samples (7 $\alpha$ -hydroxy-cholesten-3-one [7 $\alpha$ C4], fibroblast growth factor 19 [FGF-19], autotaxin, progesterone sulfate, and glucagon-like peptide 1 [GLP-1]) are provided in [Table 3](#).

The analysis windows for lipid panel and glycated albumin are provided in [Table 4](#).

The analysis windows for vitamin A, D, and E levels and fetal ultrasound are provided in [Table 5](#).

**Table 2 Analysis Visit Windows for ItchRO^, sBA, Hematology\*, Chemistry\*, Coagulation\*, Weight, Vital Signs, and Urinalysis**

Nominal Visit	Nominal Study Day	Lower Limit	Upper Limit
Baseline	1	(none)	1
Week 1	8	2	11
Week K (K is every week after previous visit)	K*7 + 1	K*7 – 2	K*7 + 4

^ ItchRO is collected daily, but will have weekly averages calculated and results will be grouped according to the analysis windows above.

\* Hematology, chemistry, and coagulation are not planned to be collected at the baseline visit. Rather, the screening visit (or a subsequent unscheduled visit) will serve as the baseline.

**Table 3 Analysis Visit Windows for 5-D Itch, CSS, EQ-5D-5L, PROMIS Fatigue and Sleep PROs, PIS-Itch, PGIC-Itch, and Biomarker Samples (C4, FGF-19, Autotaxin, Progesterone Sulfate, GLP-1)**

Nominal Visit	Nominal Study Day	Lower Limit	Upper Limit
Baseline*	1	(none)	1
Week 3	22	19	25

\*PGIC-Itch was not collected at baseline.

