## **7.6. Changes From Protocol-Specified Safety Analyses**

There are no deviations from the protocol-specified safety analyses.

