### 13. APPENDIX 1 SCHEDULE OF ACTIVITIES

**Table 7 Schedule of Activities**

Visit Name	Screening	Treatment Period				Follow-Up		Notes
		Baseline	Week 1, 2, 3, etc.	Early Term*	EOT/Delivery	F1	F2 (EOS)	
Day/Week (Window)	Day -10 to -1	0*	Every 7 Days (±1 Day) Until Delivery		Day of Delivery (+2 Days)	Phone Call: 14 Days after Delivery (±2 Days)	Clinic Visit: 28 Days after Delivery (±3 Days)	*Participants who early terminate from study drug should still continue with weekly visits through delivery, F1, and F2.  Some visits may be conducted as a home health or remote visit at the discretion of the investigator upon approval by the medical monitor or designee and in accordance with local and regional regulations.  *Regardless of date of screening visit, baseline visit must occur no later than 35 weeks and 0 days gestational age.
Administrative Procedures								
Informed consent	X							
Eligibility Procedures								
Inclusion/exclusion criteria	X	X						
Demography	X							
Prior/concomitant treatment	X	X	X	X	X	X	X	
Medical history	X	X						Includes menstrual and obstetric history
Estimated gestational age assessment	X							Confirmation of eligibility based upon estimated gestational age required before randomization: CRL from early ultrasound or head circumference on ultrasound if CRL is >84 mm.
Hepatitis and HIV screen, TSH	X							
Dosing Procedures								
Randomization		X						
Study treatment dispensing		X	X					As needed
Study treatment collection/reconciliation			X	X	X			As needed

Visit Name	Screening	Treatment Period				Follow-Up		Notes
		Baseline	Week 1, 2, 3, etc.	Early Term*	EOT/Delivery	F1	F2 (EOS)	
Day/Week (Window)	Day -10 to -1	0*	Every 7 Days (±1 Day) Until Delivery		Day of Delivery (+2 Days)	Phone Call: 14 Days after Delivery (±2 Days)	Clinic Visit: 28 Days after Delivery (±3 Days)	
*Participants who early terminate from study drug should still continue with weekly visits through delivery, F1, and F2.
 
Some visits may be conducted as a home health or remote visit at the discretion of the investigator upon approval by the medical monitor or designee and in accordance with local and regional regulations.
 
*Regardless of date of screening visit, baseline visit must occur no later than 35 weeks and 0 days gestational age.

Efficacy Procedures								

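### SAP 7.2 leaves F2 and late post-discontinuation laboratory results listed but not tabulated, and SAP Table 2, read literally, files other F2 measurements under pregnancy week windows

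*SAP*

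**What the plan says.** **Laboratory cut-off.** SAP 7.2 says that laboratory summaries "will include data collected up to the last dose of study drug plus 7 days for participants who have permanently discontinued study drug". The only other class it names is participants still ongoing at an interim snapshot, for whom all available data are used. The same section promises a by-participant listing of hematology, serum chemistry and urinalysis.

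**Timing.** SAP 1.2 states: "Study treatment dosing will begin on Day 1 and continue until end of the study treatment period, defined as the day of delivery". The schedules in SAP Table 7 and protocol Table 1 put F2 at 28 ± 3 days after delivery. Both mark hematology, chemistry, coagulation, vitamins, lipids, urinalysis, weight, vital signs and sBA at F2. Both also keep a woman who stops study drug early on weekly visits through delivery and then F2.

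**Protocol commitment.** Protocol 10.4.2.3 tabulates laboratory values by scheduled visit and adds: "Participants with clinical laboratory values outside of the normal reference range at any postbaseline assessment will be summarized". It gives no time limit. SAP 7.6 states: "There are no deviations from the protocol-specified safety analyses".

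**Visit windows.** SAP 3.8.2 assigns observations to analysis windows and names a single exception: "A notable exception to the analysis visit windows below is the end of treatment/date of delivery". Table 2 continues Week K without an upper limit and has no F2 row. Tables 4 and 5 have the same structure on 2-week and 4-week cycles. SAP 7.3 summarises weight and vital signs at every postbaseline time point and states no last-dose limit.

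**The concern.** Two rules, each sensible alone, handle the follow-up visit badly.

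The first removes results from the tables. A woman who stops drug early, for instance after a liver signal, keeps having blood drawn, but nothing after day 7 reaches a summary or shift table. SAP 7.2.2 calls a participant normal when all her postbaseline results are in range. With the 7.2 cut-off applied, she could be shown as normal although a later value was abnormal. Vitamins are the sparsest case. Fat-soluble vitamin deficiency is an event of clinical interest, yet postbaseline vitamins are drawn only every 4 weeks from Week 4, at delivery and at F2. A woman who delivers before Week 4 has two scheduled postbaseline draws, and the cut-off leaves one in the tables. Protocol 4.3.2.1 expects relatively few participants to stay on treatment beyond 3 weeks.

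The second rule does the opposite for weight and vital signs. No cut-off applies and no F2 visit is defined, so postpartum values take the label of a pregnancy week and are averaged with values from women still pregnant. If sBA is handled this way too, the protocol's own background matters: "After delivery, there is rapid (within a few weeks) resolution of signs and symptoms". Late-week descriptive sBA would then fall partly because women had delivered.

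**Working it through.** **1. Check the window rule against the SAP's own figures.** Table 2 gives Week K = study days 7K − 2 to 7K + 4.
- K = 3: 21 − 2 = 19 to 21 + 4 = 25, the Week 3 limits in Table 3.
- K = 2: upper limit 14 + 4 = 18, as in the Day 18 example in SAP 3.8.3.
- K = 1: upper limit 7 + 4 = 11, as in Table 2.

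**2. F2 against the laboratory cut-off.** The last dose is on the day of delivery at the latest. F2 is 28 − 3 = 25 to 28 + 3 = 31 days after delivery. The limit is 7 days, so F2 is at least 25 − 7 = 18 days beyond it.

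There is one exception. Under SAP 4.2.1 a missing last-dose date is replaced by the latest of several contact dates, which can be F2 itself. F2 results would then pass.

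**3. Where F2 lands in Table 2.** For delivery on study day D, F2 is on day D + 25 to D + 31. If D = 7j + 1, that is 7(j + 4) − 2 to 7(j + 4) + 4, which is exactly the Week j + 4 window.

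| Delivery day | F2 days | Window |
|---|---|---|
| 8 | 33–39 | Week 5 |
| 15 | 40–46 | Week 6 |
| 22 | 47–53 | Week 7 |
| 29 | 54–60 | Week 8 |
| 36 | 61–67 | Week 9 |

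Other delivery days straddle two windows: D = 18 gives days 43–49, Weeks 6 and 7.

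**4. Who shares a window.** Take entry at 36w0d and delivery at 39w0d (assumed). Then D = 3 × 7 + 1 = 22 and F2 is in Week 7. A woman who entered at 31w0d and is still pregnant on Day 50 (31w0d + 49 days = 38w0d) has her Week 7 visit on that day. The two values would be averaged together.

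**5. Earliest reach.** With D = 1, the first possible F2 is 1 + 25 = Day 26, the first day of Week 4 (26–32). The Week 3 window ends on Day 25, so no F2 value can enter it.

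**6. Illustrative postpartum share.** The documents give no joint distribution of entry and delivery. The assumptions here are uniform gestational ages, at least 1 week on study, F2 at D + 28, and weekly visits on the nominal day with none missed. Share = F2 records in the window ÷ (F2 records + women still pregnant at the Week K visit). Simulation gives approximately:

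| Entry / delivery (weeks) | Week 5 | Week 6 |
|---|---|---|
| 32–36 / 36–39 | 30% | 85% |
| 32–36 / 37–40 | 4% | 38% |
| 28–36 / 36–39 | 5% | 17% |

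In the first scenario every record from Week 7 on is postpartum. In the third the share is about 29%, 42% and 64% in Weeks 7, 8 and 9.

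**The case against.** Last dose + 7 days is a recognised on-treatment convention, and it matches the window for treatment-emergent adverse events in protocol 10.4.2.1 and SAP 7.1.5.1. It deserves to stay. Simply replacing it with all postbaseline values would put postpartum results into the main shift table, which is the same kind of mixing criticised in Table 2.

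A reader might infer that recovery is never shown. The documents do not support that. The cut-off governs summaries only, SAP 7.2 provides a listing, and protocol 10.4.2 lists all safety data. Protocol 8.4.7 also requires clinically significant laboratory values to be repeated until they return to normal or baseline or cease to be significant. What stands is that listings do not compare arms.

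A reader might also infer that SAP 7.6 is a false declaration. SAP 1 says the plan rests on protocol Version 1 of 14 October 2020, which is not supplied, and it describes a different Part 1. The conflict with the current protocol 10.4.2.3 is real, but it may only show that the SAP is out of date.

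The Week K filing is an inference from a missing row. Table 2 nowhere calls Week K on-treatment, and the schedules show weekly visits running only until delivery, with F2 in a separate column. A programmer could reasonably keep F2 apart. But the SAP tells her to assign observations to windows and excepts only delivery, so the literal result is the one shown.

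For sBA the outcome is undetermined. SAP Table 7 places it among the safety procedures. If 7.2 covers it, F2 sBA is dropped from the summaries and not misfiled.

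One could also say that a woman who delivers has completed drug and not discontinued it. Section 7.2 offers only two classes, however, and at the final analysis she fits no other.

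**Conclusion.** The point holds as a fault of safety tabulation and descriptive display.

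- **Laboratory results.** F2 results, and those more than 7 days after an early stop, are left out of summary and shift tables that the current protocol plans by scheduled visit and for any postbaseline assessment. This rests on the last-dose date being recorded and on women who have delivered counting as permanently off drug.
- **Weight and vital signs.** Read literally, F2 values enter week windows from Week 4 on. The direction follows from the date arithmetic. The size does not: the Week 5 share runs from about 4% to 30% in the illustrations, and only the latest weeks become wholly postpartum.
- **sBA.** Either dropped or misfiled at F2; the SAP must say which. A reader might infer that efficacy results would show a spurious sustained fall in sBA. They would not. The primary model stops at Week 3, end-of-treatment sBA uses the delivery value as its own visit, and only by-visit descriptive statistics are exposed, in both arms.

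The Week 3 sBA and ItchRO analyses and the composite perinatal endpoint are unaffected. The change should be made, but the trial's main conclusions do not depend on it.

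**What to change.** 1. In SAP 3.8.2, define F2 as its own analysis visit, as EOT/delivery already is, and exclude it from every Week K window in Tables 2, 4 and 5.
2. State whether the 7-day rule applies to sBA.
3. In SAP 7.2, keep last dose + 7 days as the on-treatment summary and shift table. Add an F2 summary column, and an all-postbaseline abnormality and shift table that includes post-discontinuation values, with postpartum values shown separately.
4. Reconcile SAP 7.2 and 7.6 with the current protocol 10.4.2.3, and declare any departure that remains.

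The cost is SAP wording and a few extra table columns. No new data are needed, and the Week 3 analysis does not change.

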#### **7.2.1. Summaries of Numeric Laboratory Results**

Descriptive statistics will be provided by indication for each laboratory test specified in the study protocol as follows:

- Baseline values
- Values at each postbaseline time point
- Change and percentage change from baseline at each postbaseline time point

A baseline laboratory value will be defined as the last measurement obtained on or prior to the date/time of first dose of study drug. Change from baseline to a postbaseline visit will be

defined as the visit value minus the baseline value. The mean, median, Q1, Q3, minimum, and maximum values will be displayed to the reported number of digits; SD values will be displayed to the reported number of digits plus 1.

### **7.2.2. Shifts Relative to the Baseline Value**

For all laboratory tests, shift tables will be presented by showing changes in results from baseline value (low, normal, and high) to the worst postbaseline result (low, normal, high, or low and high). A participant would have a worst postbaseline result of normal if all postbaseline results are within the normal reference range. The value of “low and high” would be used if the participant has postbaseline values that are below the normal reference range at one visit and above the normal reference range at another visit.

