### 3.1. Primary Objective and Endpoint

Part 1:

- To assess the safety and tolerability of volixibat in participants with ICP on the basis of the following endpoints:
  - Proportion of participants experiencing one or more of the following:
    - Treatment-emergent adverse events (TEAEs), serious adverse events (SAEs), adverse events of special interest (AESIs), events of clinical interest (ECIs), and AEs that lead to discontinuation of study drug
    - Clinically significant laboratory abnormalities

Part 2:

- To assess the efficacy of volixibat on the reduction of elevated sBA concentrations in participants with ICP on the basis of the following endpoint:
  - Mean change from baseline to Week 3 of the treatment period in total sBA concentration

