#### 8.4.7. Clinical Laboratory Evaluations

Refer to [Appendix 1](#) for the list of clinical laboratory tests to be performed and to the SoA ([Table 1](#)) for the timing and frequency. The investigator must review the laboratory report, document this review, and record any clinically relevant changes occurring during the study in the AE section of the eCRF. The laboratory reports must be filed with the source documents. Clinically significant abnormal laboratory findings are those that are not associated with an underlying disease.

All laboratory tests with values considered clinically significantly abnormal during participation in the study or within 7 ( $\pm 2$ ) days after the last dose of study drug should be repeated until the values return to normal or baseline or are no longer considered clinically significant by the investigator or medical monitor.

If such values do not return to normal/baseline within a period of time judged reasonable by the investigator, the etiology should be identified and the sponsor notified.

All protocol-required laboratory assessments, as defined in [Appendix 1](#), must be conducted in accordance with the SoA ([Table 1](#)).

If laboratory values from non-protocol-specified laboratory assessments performed at a local laboratory require a change in participant management or are considered clinically significant by the investigator (e.g., SAE or AE), then the results must be recorded in the eCRF. The investigators will maintain a copy of the reference ranges (with the record of the reference ranges) for the local laboratory(ies) used.

All clinical laboratory assays will be performed according to the laboratory's normal procedures. Reference ranges are to be supplied by the laboratory and will be used to assess the clinical laboratory data for clinical significance and out-of-range pathological changes. The investigator should assess out-of-range clinical laboratory values for clinical significance, indicating if the value(s) is/are not clinically significant or clinically significant. Abnormal clinical laboratory values that are unexpected or not explained by the participant's clinical condition may, at the discretion of the investigator or sponsor, be repeated as soon as possible until confirmed, explained, or resolved.

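### SAP 7.2 plans no CTCAE-graded or threshold-based laboratory summary, so the laboratory-abnormality endpoint and the graded summary in protocol 10.4.2.3 have no matching output, although SAP 7.6 declares no deviations.

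*SAP*

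**What the plan says.** The endpoint is named three times. Protocol 3.1 lists "Clinically significant laboratory abnormalities" within the Part 1 primary endpoint, protocol 3.3 makes their incidence a Part 2 safety endpoint, and SAP 1.1.3 repeats it.

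Protocol 10.4.2.3 says that central-laboratory values, "where grading criteria apply, will be graded according to the CTCAE grading scale". It adds that participants with out-of-range postbaseline values will be summarized, including by CTCAE, and in a separate sentence that shifts from baseline will be tabulated.

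SAP 7.2 plans three laboratory outputs:
- Numeric summaries (7.2.1), including "Change and percentage change from baseline at each postbaseline time point". On display, "The mean, median, Q1, Q3, minimum, and maximum values will be displayed to the reported number of digits".
- A categorical table (7.2.2): "shift tables will be presented by showing changes in results from baseline value (low, normal, and high) to the worst postbaseline result". The postbaseline side has one more category, for participants both low and high at different visits.
- Chronological listings by participant.

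SAP 7.6 then states: "There are no deviations from the protocol-specified safety analyses".

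**The concern.** The endpoint is an incidence, so it needs a definition and a count of participants. SAP 7.2 gives neither, and nothing in it grades a laboratory value.

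The categorical table that does exist is weakest for the tests that matter most here. Protocol 2.1 describes ICP as marked by "elevated serum aminotransferases and sBA levels". Exclusion criterion 15 removes ALT or AST only from 5 x ULN upward, and protocol Appendix 3 has a separate liver algorithm for women whose ALT, AST or bilirubin is abnormal at baseline. Many participants may therefore start in the high category and have nowhere further to move.

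Part 1 informs the choice between 20 mg and 80 mg BID, and Part 2 compares the chosen dose with placebo. What is at stake is whether graded hepatic worsening is counted by arm from laboratory data, or has to be pieced together from visit summaries, listings and adverse event reports.

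**Working it through.** The plan gives no figure on this point to reproduce. The check sets the commitments beside the outputs, then tests what each output can show.

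**1. Commitments against outputs**

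| Commitment | Output in SAP 7.2 |
|---|---|
| Incidence of clinically significant laboratory abnormalities (protocol 3.1, 3.3; SAP 1.1.3) | No definition, no incidence table |
| Summary of out-of-range participants, including by CTCAE (protocol 10.4.2.3) | None |
| Shifts from baseline tabulated (protocol 10.4.2.3) | Low/normal/high table, SAP 7.2.2 |

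**2. What the shift table shows**

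The ALT values below are assumed, in multiples of ULN, and all baselines lie below the exclusion limit of 5. A value above 1 is high. Change = worst − baseline; percentage change = 100 × (worst/baseline − 1).

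| Baseline | Worst | Shift cell | Change | Percentage change |
|---|---|---|---|---|
| 2 | 2 | high to high | 0 | 0% |
| 2 | 6 | high to high | +4 | +200% |
| 2 | 8 | high to high | +6 | +300% |
| 2 | 20 | high to high | +18 | +900% |
| 4.9 | 25 | high to high | +20.1 | +410% |
| 0.8 | 1.1 | normal to high | +0.3 | +38% |
| 0.8 | 20 | normal to high | +19.2 | +2400% |

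From a normal baseline the table registers that a rise occurred but not its size. From a raised baseline it registers nothing. The third row reaches 8/2 = 4 times baseline. That is beyond the 3-times-baseline level that Appendix 3 lists for a baseline of at least 2 x ULN, yet it looks the same as the first row.

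**3. What the numeric summaries recover**

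The last two columns are what SAP 7.2.1 would pick up, if the peak is the value used for a visit. Two limits apply.
- These are distributions by visit. They do not count participants above any threshold.
- SAP 3.8.3 keeps the record closest to the nominal day when one value per window is needed. For Week 3, SAP Table 2 gives nominal day 3×7+1 = 22 and a window from 3×7−2 = 19 to 3×7+4 = 25. With chemistry on Days 22 and 24, Day 22 is used, and a peak on Day 24 drops out of the visit statistics. Appendix 3 calls for repeat liver tests two to three times a week under close observation, so such extra samples are expected in exactly these women.

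The shift table is the only planned laboratory summary that takes the worst value, and it has the ceiling shown in step 2.

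**4. What the adverse event route recovers**

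Transaminase increases of Grade 3 or higher are an event of clinical interest (protocol 9.2.7; SAP Appendix 2, whose term list also covers bilirubin). They are tabulated (SAP 7.1.6.1) and compared by risk difference with an exact 95% CI (SAP 7.1.7). Entry to those tables requires an adverse event report. Protocol 8.4.7 states: "Clinically significant abnormal laboratory findings are those that are not associated with an underlying disease". Protocol 9.1.1 excludes disease-associated laboratory findings from adverse events unless the investigator judges them more severe than expected. A liver-test rise in ICP is a natural candidate for attribution to the disease.

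**5. Size**

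The documents do not give the fraction f entering with ALT above ULN. Assume f = 0.30 to 0.60 and that everyone randomized is dosed.
- Part 2, 100 per arm: 100 × 0.30 = 30 to 100 × 0.60 = 60 women per arm.
- Part 1, up to 80 randomized 1:1, so 40 per arm: 40 × 0.30 = 12 to 40 × 0.60 = 24 per arm.

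For these women the shift table cannot register an upward ALT change. The ceiling itself does not depend on f.

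**The case against.** The strongest reply is that the SAP is not blind to liver tests. Change, percentage change and maxima are planned for every test, every value is listed, and a Grade 3 or higher transaminase event reaches a categorical table with a between-arm comparison. The attribution filter also has limits. Protocol 9.1.1 counts a laboratory abnormality as clinically significant if, among other criteria, it requires interruption of study drug, and the rise from 2 to 8 x ULN crosses an Appendix 3 interruption level. It would escape reporting only if it were also judged disease-associated and no worse than expected. All of this stands. A reader might infer that a participant with raised ALT can rise to any level without registering anywhere; the documents do not support that.

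Second, protocol 10.4.2.3 asks for CTCAE summaries and for shift tables in separate sentences. It does not require shifts between grades, and SAP 7.2.2 satisfies the shift sentence. This stands, and it is why the table should be supplemented and not replaced. Low/normal/high is also still needed for tests without CTCAE criteria.

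Third, the SAP says it is based on protocol Version 1 of 14 October 2020 and describes a different, double-blind three-arm Part 1. A reader might infer that SAP 7.6 was false when written. That cannot be shown, because the laboratory section of Version 1 is not available. The age of the SAP may explain the gap, but it does not close it.

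Fourth, Part 1 is open label with sponsor safety monitoring, a data review after about every 20 participants, weekly chemistry and the Appendix 3 actions. A reader might infer that a dose-related hepatic signal would go unseen. These safeguards make that too strong. They do not, however, supply the reported analysis of a named endpoint.

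**Conclusion.** The point holds as a gap between commitments and outputs. Two items have no matching output in SAP 7.2: the CTCAE summary in protocol 10.4.2.3 and the incidence of clinically significant laboratory abnormalities, part of which belongs to the Part 1 primary endpoint. Against the current protocol, the statement in SAP 7.6 is inaccurate. The one worst-value laboratory table cannot show the size of a rise in women whose ALT, AST or bilirubin is already high.

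It would go too far to say that the endpoint can never be seen: abnormalities judged significant can reach the adverse event tables. That route is incomplete because it depends on attribution, and it gives no dedicated result. Nor do the documents settle which CTCAE grade the worked example reaches, since they give no CTCAE cut-offs.

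The estimate of 30 to 60 women per Part 2 arm (12 to 24 per Part 1 arm) rests on the assumed 30% to 60% with raised baseline ALT. The rest of the conclusion does not. This should be fixed before the Part 1 analysis; it does not affect the primary efficacy inference in Part 2.

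**What to change.** Keep the low/normal/high shift table and add to SAP 7.2:

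1. For tests with grading criteria, tables of baseline CTCAE v5.0 grade against worst postbaseline grade, by arm, using all central-laboratory values including unscheduled ones.
2. For ALT, AST and total bilirubin, the number and percentage of participants by arm reaching stated multiples of ULN and, for those abnormal at baseline, the baseline multiples already in protocol Appendix 3. These serve only as reporting cut-points and change no clinical rule. Appendix 3 lists no on-treatment AST multiple, so the sponsor would have to prespecify one for reporting.
3. An incidence table for the named endpoint using the protocol's investigator-judged definition (8.4.7, 9.1.1), shown beside the graded counts, which ignore attribution. Redefining the endpoint itself as a grade threshold is not needed. The SAP should say where the investigator's judgement is held in the database; protocol 8.4.7 asks for it but does not clearly require its entry in the eCRF other than through adverse events.

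Reconcile SAP 7.6 with the current protocol.

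The cost is SAP text and a few tables, mostly from central-laboratory data already collected. The downside is small: some of the counted abnormalities will reflect ICP and not study drug, in both arms.
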